9.1 ADVERSE EVENTS

The potential risks to patients of the research may include a fall (either in the HAH setting or inpatient setting), hospital acquired infection for patients randomised to inpatient admission, hospital admission for those randomised to HAH, post-discharge hospitalisation and death for all patients. All SAEs occurring during the study, either observed by the recruiting clinician or reported by the patient, will be recorded on the AE Log CRF and SAE Log CRF. All SAEs will be recorded whether or not attributed to the HAH with CGA intervention. All SAEs will be forwarded by the site to the PC-CTU and the trial manager, using the "PC-CTU SAE Report Form" following assessment for seriousness by the site clinician. Adverse events will be summarised descriptively according to randomised group, no statistical comparison will be undertaken on this data.

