6) Known cognitive decline at baseline (IQCODE)

The Short Form of the Informant Questionnaire on Cognitive Decline in the Elderly (IQCODE) [4] is assessed at the patients baseline visit only. IQCODE is a 16 item questionnaire (variables *iqcode1 – iqcode16*), each question has a possible range of scores from 1 to 5. To obtain the mean IQCODE score for each participant take the mean of all IQCODE items available for that participant. Participants will still have their mean IQCODE score calculated if they are missing several items, participants will only be missing their mean IQCODE score if they are missing every item. Randomisation was stratified by IQCODE score ≥ 3.5

7) Quality of life at baseline and 6 months

Quality of life is measured by EQ-5D-5L scores [5], and is assessed at baseline and 6 months follow-up. EQ-5D-5L index scores will be computed as per the EQ-5D-5L user guide (version 2.1 April 2015).

8) Quality adjusted survival at 6 months and 12 months

Quality adjusted survival will be analysed as part of the economic evaluation and the methods will be detailed in a separate analysis plan.

9) Length of hospital stay over 6 months from randomisation

Number of nights spent in hospital between baseline and 6 months follow-up is collected on the health service use CRF.

10) Readmission or transfer to hospital at 1 month and 6 months

Subsequent admissions to hospital is measured at 1 month, and 6 months follow-up (variable *hadmityn*). Subsequent admissions to hospital is a binary variable (0 = No, 1 = Yes). The 6 months admission to hospital data will include the data collected at the 1 month time point. Number of days spent in hospital at 1 month, and 6 months after baseline will not be considered in the main statistical analysis, this data will be analysed as part of the economic evaluation and the methods will be detailed in a separate analysis plan.

11) Resource use (health and social care and informal care) at baseline and 6 months

Resource use will be analysed as part of the economic evaluation and the methods will be detailed in a separate analysis plan.

12) Costs and cost-effectiveness

Costs and cost-effectiveness will be analysed as part of the economic evaluation and the methods will be detailed in a separate analysis plan.

13) 'Living at home' at 12 months

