9 SAFETY ANALYSIS

All patients randomised will be included in the safety analysis.

All serious adverse events (SAE) occurring during the trial enrolment period shall be detailed and reported by randomised group. The overall incidence of patients experiencing at least one SAE will be compared between the randomised groups using a chi-squared test and the difference in proportions with 95% confidence intervals will be presented. Where a patient reports more than one of the same type of event, separate tables will be presented showing a) counts of events and b) counts of patients experiencing at least one type of this event.

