13 APPENDICES

Appendix I. Schedule of study procedures

Procedures	Visit					
	Baseline	3 days	5 days	1 month	6 months	12 months
Informed consent	X					
Eligibility assessment	X	X	X		X	X
Randomisation	X					
Demographics	X					
Medical history	X					
Physical examination (where judged clinically appropriate)	X					
Trial specific questionnaires	X ¹²³	X ²	X ²	X ²	X ³	
Health resource questionnaire	X				X	
Patient feedback questionnaire				X		
Adverse event assessment		X	X		X	X

¹ Short form of the informant questionnaire on cognitive decline in the elderly measured at baseline only

² Confusion assessment method measured at baseline, 3 days, 5 days, and 1 month only.

³ Barthel index of activities of daily living, Charlson comorbidity index, Montreal cognitive assessment and EQ-5D-5L measured at baseline and 6 months only.

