Appendix II. Outcome assessment schedule

Outcomes	Visits					
	Baseline	3 days	5 days	1 month	6 months	12 months
Demographics	X					
Medical history	X					
Barthel index of activities of daily living (Barthel)	X				X	
Confusion assessment method (CAM)	X	X	X	X		
Charlson comorbidity index	X				X	
Health resource questionnaire	X				X	
Short form of the informant questionnaire on cognitive decline in the elderly (IQCODE short)	X					
Montreal cognitive assessment (MOCA)	X				X	
EQ-5D-5L (UK English)	X				X	
Adverse event assessments		X	X		X	X
Collection of mortality/living at home	X	X	X	X	X	X

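### No adverse-event assessment is scheduled at the 1-month contact, and the SAE test is not linked to the trial's own death and admission data

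*SAP*

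**What the plan says.** **Recording.** Section 9.1 states that "All SAEs occurring during the study, either observed by the recruiting clinician or reported by the patient, will be recorded", whether or not they are attributed to the intervention. The site clinician assesses seriousness, and the site forwards the report to the trials unit. The risks it names are falls, hospital-acquired infection, hospital admission from hospital at home (HAH), post-discharge hospitalisation and death.

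**Schedule.** Appendix I has a row "Adverse event assessment" and Appendix II a row "Adverse event assessments". In both, the marks stand at 3 days, 5 days, 6 months and 12 months; baseline and 1 month are blank.

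**The 1-month contact.** It does take place. Appendix I notes "Confusion assessment method measured at baseline, 3 days, 5 days, and 1 month only" and places the patient feedback questionnaire at 1 month. In Appendix II the row "Collection of mortality/living at home" is marked at every visit. Section 2.1.2 adds residential-care admission and hospital admission (*hadmityn*) at 1 month.

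**Analysis.** Section 9 includes all randomised patients and states: "The overall incidence of patients experiencing at least one SAE will be compared between the randomised groups using a chi-squared test". The difference in proportions is given with a 95% confidence interval. The SAE window in section 9 is the trial enrolment period, which is not defined; section 9.1 speaks of the whole study.

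**Parallel data.** Under section 2.1.2, vital status is taken at 3 days, 5 days, 1, 6 and 12 months (*deathyn*), with a Patient Death CRF that overrules the follow-up form. Hospital admission is taken at 1 and 6 months, and hospital nights to 6 months on the health service use CRF. Sections 9 and 9.1 mention none of these sources.

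**The concern.** The commitment is to all SAEs, but after day 5 the schedule provides no occasion to ask about them until month 6. In between, capture depends on two routes, the recruiting clinician and the patient. Both are fragile here. The patients are frail, some are enrolled through a consultee, and known cognitive decline is a stratification factor. Neither participants nor the nurses collecting outcomes are blinded (section 2.4). One arm begins care in hospital and the other at home, so who is present to see an event differs by arm.

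The SAE comparison is the only formal test in the safety section. Capture that is incomplete but equal shrinks the observed difference. Capture that differs by setting can create a difference or hide one. And because no step ties the log to the death and admission forms, the report could show more deaths or admissions as outcomes than in its safety table, with no rule for resolving the mismatch. Section 2.1.2 sets a source hierarchy for death, but only for the mortality outcome.

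**Working it through.** **1. Passages side by side**

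| Contact | AE assessment (App. I and II) | Other data at that contact |
|---|---|---|
| 3 days, 5 days | yes | CAM, vital status |
| 1 month | blank | CAM, vital status/living at home, residential care, hospital admission, feedback questionnaire |
| 6 months | yes | Barthel, MoCA, EQ-5D-5L, vital status, residential care, hospital admission |
| 12 months | yes | vital status/living at home |

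The two appendices agree, so a broken table is an unlikely explanation.

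**2. Length of the interval.** Taking 6 months as about 183 days: 183 − 5 = 178 days, and 178/183 = 97%. An assessment at 1 month (about day 30) would split this into roughly 25 and 152 days.

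**3. Arm sizes.** The SAP gives no figure on SAE capture. Its one design figure is 1050 patients at about 83% power (section 2.3). This reproduces with a two-sided continuity-corrected test of 50% vs 40% at 2:1: 329 controls, 987 in total, 987/0.94 = 1050, power 83.1%. The point does not depend on it; it supplies only 1050 × 2/3 = 700 HAH and 350 inpatient patients.

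**4. Deaths in the interval (assumed mortality).** With constant hazard λ = −ln(1 − m)/182.6, where m is 6-month mortality, deaths from day 5 to month 6 are 1050 × [m − (1 − e^(−5λ))]. Deaths before 1 month use 30.4 days as the upper limit.

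| Assumed m | Deaths, day 5 to month 6 | Of these, before 1 month |
|---|---|---|
| 10% | 102 | 15 |
| 20% | 204 | 32 |
| 30% | 305 | 50 |

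These patients have no scheduled AE assessment after day 5. On these assumptions most would still be alive at the 1-month contact.

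**5. Equal under-capture (assumed true SAE proportions 30% inpatient, 20% HAH).** With a share s of affected patients captured in both arms, the observed difference is s × 10 points. Power = Φ[(d − 1.96·SE₀)/SE₁], with SE₀ pooled and SE₁ unpooled. At s = 0.7: 21% vs 14%, SE₀ = 0.0242, SE₁ = 0.0254, so Φ[(0.07 − 0.0474)/0.0254] = 81%.

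| Capture s | Observed difference | Power |
|---|---|---|
| 100% | 10 points | 94% |
| 90% | 9 points | 91% |
| 70% | 7 points | 81% |
| 50% | 5 points | 65% |

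**6. Unequal capture (assumed true incidence 50% in both arms; 75% captured in the arm of 700).** SE = √[p₁(1 − p₁)/350 + p₂(1 − p₂)/700], z = (p₁ − p₂)/SE, and P(reject) = Φ(z − 1.96) + Φ(−z − 1.96).

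| Capture in the arm of 350 | Observed | SE | z | P(reject) |
|---|---|---|---|---|
| 75% | 37.5% vs 37.5% | 0.0317 | 0 | 5% |
| 80% | 40.0% vs 37.5% | 0.0319 | 0.78 | 12% |
| 85% | 42.5% vs 37.5% | 0.0321 | 1.56 | 34% |
| 90% | 45.0% vs 37.5% | 0.0323 | 2.32 | 64% |

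Steps 4 to 6 show direction and sensitivity only. No rate in them comes from the SAP.

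**The case against.** **Recording between visits is provided for.** Section 9.1 commits to it throughout the study, and which visits carry an AE form is commonly a protocol matter. The protocol is not shown. This stands: a blank cell is a gap in scheduled, active questioning, not a bar on SAE reporting, and the 6-month assessment may look back over the interval. It does not answer the missing link between the log and the other forms, which belongs to the analysis plan.

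**Patients are not lost from view.** A reader might infer that those who die after day 5 are never assessed again. The SAP does not support that. Anyone alive at 1 month is contacted for other measures, and deaths are recorded on follow-up forms and a death form.

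**Much of the named harm is compared elsewhere.** Mortality at 6 months and readmission or transfer at 1 and 6 months have their own models (section 5.1). This stands. The events least protected are non-fatal falls and infections that lead to no admission, and reconciliation will not recover those.

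**Silence is not exclusion.** Section 9 does not say that deaths or admissions are left out of the SAE set. True; the fault is that no rule is stated.

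**The figures prove little.** Any visit schedule leaves most days without a visit, so 97% describes the interval and does not estimate lost events. The 64% is one end of an assumed range, and unequal capture could arise even with a 1-month form. Both points stand.

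**Counting every admission as an SAE would go too far.** It would bypass the site's seriousness assessment and, where the control treatment is itself admission, would turn on how the index stay is treated. This stands and shapes the fix.

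**Conclusion.** The point holds as a modest, inexpensive improvement. Both appendices omit adverse-event assessment at a contact that takes place, and section 9 tests SAE incidence with no stated check against deaths and admissions already on file. As written, the comparison can be incomplete, can differ in capture by setting, and can conflict with the trial's own outcome tables.

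The size cannot be derived from the SAP, which gives no SAE rate, capture rate or 6-month mortality. The documents do not show that SAEs have been missed or that capture does differ by arm. A reader might also infer that the safety comparison is invalid or that most harms go unseen. That goes beyond the text, because reporting is continuous by design and death and admission are analysed as outcomes in their own right.

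**What to change.** 1. **Section 9: reconcile before testing.** Compare the SAE log with all recorded deaths (*deathyn*, Patient Death CRF) and all post-randomisation hospital admissions (*hadmityn*, health service use CRF). Send unmatched events to the site for the seriousness assessment in section 9.1; do not count them automatically. State one rule for the allocated index episode and apply it to both arms.
2. **Sections 9 and 9.1: use one window.** Define the period over which SAEs are analysed and use the same term in both sections.
3. **Appendices I and II.** For any patient still to reach it, record adverse events at the existing 1-month contact; otherwise reconcile the appendices with section 9.1 by stating how SAEs between day 5 and month 6 are ascertained. The SAP does not say how many patients have yet to reach 1 month, so this step may have little effect.

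Cost: SAP wording, a reconciliation listing from data already collected, site queries and, where still possible, one form at an existing contact. Reported SAE counts may rise in both arms. The sample size and the primary analysis do not change.

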10 VALIDATION

At a minimum the primary analysis ('living at home' at 6 months), sensitivity analysis, and safety analysis in the main statistical analysis report will be validated. The primary outcome for the secondary analysis ('living at home' at 12 months) will also be validated when available. Validation will be conducted by a trial statistician who has not performed the main analysis or authored the SAP.

11 CHANGES TO THE PROTOCOL OR PREVIOUS VERSIONS OF SAP

The primary outcome in the published protocol was originally planned to include data collected at both the 6 and 12 months' time point. However, it was decided to analyse the data collected at the two time points separately because it is now planned to potentially publish the results from the 6 months analysis before the 12 month follow-up is complete. All data that is collected at the 12 months' time point will be analysed separately from the 6 months data. In terms of the primary outcome, the analysis of both the 6 and 12 month data will be conducted as a sensitivity analysis.

The statistical analysis methods section in the published protocol states that the primary outcome of 'living at home' and other binary outcomes will be analysed using a mixed-effect logistic regression model. It has been decided to analyse the binary outcome by means of a generalised linear mixed model instead so that relative risk measures can be obtained from the model.

13 APPENDICES

Appendix I. Schedule of study procedures

Procedures	Visit					
	Baseline	3 days	5 days	1 month	6 months	12 months
Informed consent	X					
Eligibility assessment	X	X	X		X	X
Randomisation	X					
Demographics	X					
Medical history	X					
Physical examination (where judged clinically appropriate)	X					
Trial specific questionnaires	X ¹²³	X ²	X ²	X ²	X ³	
Health resource questionnaire	X				X	
Patient feedback questionnaire				X		
Adverse event assessment		X	X		X	X

¹ Short form of the informant questionnaire on cognitive decline in the elderly measured at baseline only

² Confusion assessment method measured at baseline, 3 days, 5 days, and 1 month only.

³ Barthel index of activities of daily living, Charlson comorbidity index, Montreal cognitive assessment and EQ-5D-5L measured at baseline and 6 months only.

Appendix II. Outcome assessment schedule

Outcomes	Visits					
	Baseline	3 days	5 days	1 month	6 months	12 months
Demographics	X					
Medical history	X					
Barthel index of activities of daily living (Barthel)	X				X	
Confusion assessment method (CAM)	X	X	X	X		
Charlson comorbidity index	X				X	
Health resource questionnaire	X				X	
Short form of the informant questionnaire on cognitive decline in the elderly (IQCODE short)	X					
Montreal cognitive assessment (MOCA)	X				X	
EQ-5D-5L (UK English)	X				X	
Adverse event assessments		X	X		X	X
Collection of mortality/living at home	X	X	X	X	X	X

Appendix III. Questionnaire scoring

Questionnaire	Possible range of scores	Higher or lower score indicates better health
Charlson Index (Comorbidity)	0-36	Lower
Barthel Index (Activities of daily living)	0-20	Higher
MOCA (Cognitive impairment)	0-30	Higher ≥26 is considered normal (≥18 is considered normal if visually impaired)
IQCODE short (background cognitive status)	1-5 (mean score across all questions)	Lower (3 indicates not much change in last 10 years)
EQ5D VAS (Health status)	0-100	Higher

Appendix IV. Flow diagram of trial participants
